5.3.2 Eliciting Adverse Event Information

A consistent methodology of non-directive questioning should be adopted for eliciting adverse event information at all patient evaluation timepoints. Examples of non-directive questions include the following:

"How have you felt since your last clinic visit?"

"Have you had any new or changed health problems since you were last here?"

5.3.3 Assessment of Severity of Adverse Events

The adverse event severity grading scale for the NCI CTCAE (v4.0) will be used for assessing adverse event severity. [Table 5](#) will be used for assessing severity for adverse events that are not specifically listed in the NCI CTCAE.

Table 5 Adverse Event Severity Grading Scale for Events Not Specifically Listed in NCI CTCAE

Grade	Severity
1	Mild; asymptomatic or mild symptoms; clinical or diagnostic observations only; or intervention not indicated
2	Moderate; minimal, local, or non-invasive intervention indicated; or limiting age-appropriate instrumental activities of daily living ^a
3	Severe or medically significant, but not immediately life-threatening; hospitalization or prolongation of hospitalization indicated; disabling; or limiting self-care activities of daily living ^{b, c}
4	Life-threatening consequences or urgent intervention indicated ^d
5	Death related to adverse event ^d

NCI CTCAE = National Cancer Institute Common Terminology Criteria for Adverse Events.

Note: Based on the most recent version of NCI CTCAE (v4.0), which can be found at:
http://ctep.cancer.gov/protocolDevelopment/electronic_applications/ctc.htm

^a Instrumental activities of daily living refer to preparing meals, shopping for groceries or clothes, using the telephone, managing money, etc.

^b Examples of self-care activities of daily living include bathing, dressing and undressing, feeding oneself, using the toilet, and taking medications, as performed by patients who are not bedridden.

^c If an event is assessed as a "significant medical event," it must be reported as a serious adverse event (see Section [5.4.2](#) for reporting instructions), per the definition of serious adverse event in Section [5.2.2](#).

^d Grade 4 and 5 events must be reported as serious adverse events (see Section [5.4.2](#) for reporting instructions), per the definition of serious adverse event in Section [5.2.2](#).

5.3.4 Assessment of Causality of Adverse Events

Investigators should use their knowledge of the patient, the circumstances surrounding the event, and an evaluation of any potential alternative causes to determine whether an adverse event is considered to be related to the study drug, indicating "yes" or "no" accordingly. The following guidance should be taken into consideration (see also [Table 6](#)):

- Temporal relationship of event onset to the initiation of study drug
- Course of the event, with special consideration of the effects of dose reduction, discontinuation of study drug, or reintroduction of study drug (as applicable)
- Known association of the event with the study drug or with similar treatments
- Known association of the event with the disease under study

- Presence of risk factors in the patient or use of concomitant medications known to increase the occurrence of the event
- Presence of non-treatment-related factors that are known to be associated with the occurrence of the event

Table 6 Causal Attribution Guidance

Is the adverse event suspected to be caused by the study drug on the basis of facts, evidence, science-based rationales, and clinical judgment?	
YES	There is a plausible temporal relationship between the onset of the adverse event and administration of the study drug, and the adverse event cannot be readily explained by the patient's clinical state, intercurrent illness, or concomitant therapies; and/or the adverse event follows a known pattern of response to the study drug; and/or the adverse event abates or resolves upon discontinuation of the study drug or dose reduction and, if applicable, reappears upon re-challenge.
NO	An adverse event will be considered related, unless it fulfills the criteria specified below. Evidence exists that the adverse event has an etiology other than the study drug (e.g., preexisting medical condition, underlying disease, intercurrent illness, or concomitant medication); and/or the adverse event has no plausible temporal relationship to administration of the study drug (e.g., cancer diagnosed 2 days after first dose of study drug).

For patients receiving combination therapy, causality will be assessed individually for each protocol-mandated therapy.

5.3.5 Procedures for Recording Adverse Events

Investigators should use correct medical terminology/concepts when recording adverse events on the Adverse Event eCRF. Avoid colloquialisms and abbreviations.

Only one adverse event term should be recorded in the event field on the Adverse Event eCRF.

5.3.5.1 Infusion-Related Reactions

Adverse events that occur during or within 24 hours after study drug administration and are judged to be related to study drug infusion should be captured as a diagnosis (e.g., "infusion-related reaction" or "anaphylactic reaction") on the Adverse Event eCRF. If possible, avoid ambiguous terms such as "systemic reaction." Associated signs and symptoms should be recorded on the dedicated Infusion-Related Reaction eCRF. If a patient experiences both a local and systemic reaction to the same dose of study drug, each reaction should be recorded separately on the Adverse Event eCRF, with signs and symptoms also recorded separately on the dedicated Infusion-Related Reaction eCRF.

5.3.5.2 Diagnosis versus Signs and Symptoms

A diagnosis (if known) should be recorded on the Adverse Event eCRF rather than individual signs and symptoms (e.g., record only liver failure or hepatitis rather than jaundice, asterixis, and elevated transaminases). However, if a constellation of signs and/or symptoms cannot be medically characterized as a single diagnosis or syndrome at the time of reporting, each individual event should be recorded on the Adverse Event eCRF. If a diagnosis is subsequently established, all previously reported adverse events based on signs and symptoms should be nullified and replaced by one adverse event report based on the single diagnosis, with a starting date that corresponds to the starting date of the first symptom of the eventual diagnosis.

5.3.5.3 Adverse Events That Are Secondary to Other Events

In general, adverse events that are secondary to other events (e.g., cascade events or clinical sequelae) should be identified by their primary cause, with the exception of severe or serious secondary events. A medically significant secondary adverse event that is separated in time from the initiating event should be recorded as an independent event on the Adverse Event eCRF. For example:

- If vomiting results in mild dehydration with no additional treatment in a healthy adult, only vomiting should be reported on the eCRF.
- If vomiting results in severe dehydration, both events should be reported separately on the eCRF.
- If a severe gastrointestinal hemorrhage leads to renal failure, both events should be reported separately on the eCRF.
- If dizziness leads to a fall and consequent fracture, all three events should be reported separately on the eCRF.
- If neutropenia is accompanied by an infection, both events should be reported separately on the eCRF.

All adverse events should be recorded separately on the Adverse Event eCRF if it is unclear as to whether the events are associated.

5.3.5.4 Persistent or Recurrent Adverse Events

Persistent Adverse Events First Reported in Study GA40209 or in Parent Study

A persistent adverse event is one that extends continuously, without resolution, between patient evaluation timepoints. Such events should only be recorded once on the Adverse Event eCRF. The initial severity (intensity or grade) of the event will be recorded at the time the event is first reported. If a persistent adverse event becomes more severe, the most extreme severity should also be recorded on the Adverse Event eCRF. Details regarding any increases or decreases in severity will be captured on the Adverse Event Intensity or Grade Changes eCRF. If the event becomes serious, it should be reported to the Sponsor immediately (i.e., no more than 24 hours after learning that the event became serious; see Section [5.4.2](#) for reporting instructions).

The Adverse Event eCRF should be updated by changing the event from "non-serious" to "serious," providing the date that the event became serious, and completing all data fields related to serious adverse events.

Persistent Adverse Events First Reported in the Parent Study

An adverse event that is ongoing at the end of a parent study will be marked as not resolved in the eCRF for that study and will be reopened in Study GA40209 with the same start date, adverse event term, and severity recorded in the parent study. The severity (NCI CTCAE grade) should be evaluated by the investigator at the start of Study GA40209 and updated in the Adverse Event Intensity or Grade Changes eCRF if applicable.

Recurrent Adverse Events

A recurrent adverse event is one that resolves between patient evaluation timepoints and subsequently recurs. Each recurrence of an adverse event should be recorded as a separate event on the Adverse Event eCRF.

5.3.5.5 Abnormal Laboratory Values

Not every laboratory abnormality qualifies as an adverse event. A laboratory test result must be reported as an adverse event if it meets any of the following criteria:

- Is accompanied by clinical symptoms
- Results in a change in study treatment (e.g., dosage modification, treatment interruption, or treatment discontinuation)
- Results in a medical intervention (e.g., potassium supplementation for hypokalemia) or a change in concomitant therapy
- Is clinically significant in the investigator's judgment

It is the investigator's responsibility to review all laboratory findings. Medical and scientific judgment should be exercised in deciding whether an isolated laboratory abnormality should be classified as an adverse event.

If a clinically significant laboratory abnormality is a sign of a disease or syndrome (e.g., ALP and bilirubin 5× ULN associated with cholestasis), only the diagnosis (i.e., cholestasis) should be recorded on the Adverse Event eCRF.

If a clinically significant laboratory abnormality is not a sign of a disease or syndrome, the abnormality itself should be recorded on the Adverse Event eCRF, along with a descriptor indicating whether the test result is above or below the normal range (e.g., "elevated potassium," as opposed to "abnormal potassium"). If the laboratory abnormality can be characterized by a precise clinical term per standard definitions, the clinical term should be recorded as the adverse event. For example, an elevated serum potassium level of 7.0 mEq/L should be recorded as "hyperkalemia."

Observations of the same clinically significant laboratory abnormality from visit to visit should only be recorded once on the Adverse Event eCRF (see Section [5.3.5.4](#) for details on recording persistent adverse events).

5.3.5.6 Abnormal Vital Sign Values

Not every vital sign abnormality qualifies as an adverse event. A vital sign result must be reported as an adverse event if it meets any of the following criteria:

- Is accompanied by clinical symptoms
- Results in a change in study treatment (e.g., dosage modification, treatment interruption, or treatment discontinuation)
- Results in a medical intervention or a change in concomitant therapy
- Is clinically significant in the investigator's judgment

It is the investigator's responsibility to review all vital sign findings. Medical and scientific judgment should be exercised in deciding whether an isolated vital sign abnormality should be classified as an adverse event.

If a clinically significant vital sign abnormality is a sign of a disease or syndrome (e.g., high blood pressure), only the diagnosis (i.e., hypertension) should be recorded on the Adverse Event eCRF.

Observations of the same clinically significant vital sign abnormality from visit to visit should only be recorded once on the Adverse Event eCRF (see Section [5.3.5.4](#) for details on recording persistent adverse events).

5.3.5.7 Abnormal ECG Findings

Not every ECG abnormality qualifies as an adverse event. An ECG finding must be reported as an adverse event if it meets any of the following criteria:

- Is accompanied by clinical symptoms
- Results in a change in study treatment (e.g., dosage modification, treatment interruption, or treatment discontinuation)
- Results in a medical intervention or a change in concomitant therapy
- Is clinically significant in the investigator's judgment

It is the investigator's responsibility to review all ECG findings. Medical and scientific judgment should be exercised in deciding whether an isolated ECG abnormality should be classified as an adverse event.

If a clinically significant ECG abnormality is a sign of a disease or syndrome (e.g., high blood pressure), only the diagnosis should be recorded on the Adverse Event eCRF.

Observations of the same clinically significant ECG abnormality from visit to visit should only be recorded once on the Adverse Event eCRF (see Section 5.3.5.4 for details on recording persistent adverse events).

5.3.5.8 Abnormal Liver Function Tests

The finding of an elevated ALT or AST ($>3 \times \text{ULN}$) in combination with either an elevated total bilirubin ($>2 \times \text{ULN}$) or clinical jaundice in the absence of cholestasis or other causes of hyperbilirubinemia is considered to be an indicator of severe liver injury (as defined by Hy's Law). Therefore, investigators must report as an adverse event the occurrence of either of the following:

- Treatment-emergent ALT or AST $>3 \times \text{ULN}$ in combination with total bilirubin $>2 \times \text{ULN}$
- Treatment-emergent ALT or AST $>3 \times \text{ULN}$ in combination with clinical jaundice

The most appropriate diagnosis or (if a diagnosis cannot be established) the abnormal laboratory values should be recorded on the Adverse Event eCRF (see Section 5.3.5.2) and reported to the Sponsor immediately (i.e., no more than 24 hours after learning of the event), either as a serious adverse event or an adverse event of special interest (see Section 5.4.2).

5.3.5.9 Deaths

All deaths that occur during the protocol-specified adverse event reporting period (see Section 5.3.1), regardless of relationship to study drug, must be recorded on the Adverse Event eCRF and immediately reported to the Sponsor (see Section 5.4.2). This includes death attributed to progression of UC or CD.

Death should be considered an outcome and not a distinct event. The event or condition that caused or contributed to the fatal outcome should be recorded as the single medical concept on the Adverse Event eCRF. Generally, only one such event should be reported. If the cause of death is unknown and cannot be ascertained at the time of reporting, "**unexplained death**" should be recorded on the Adverse Event eCRF. If the cause of death later becomes available (e.g., after autopsy), "unexplained death" should be replaced by the established cause of death. The term "**sudden death**" should not be used unless combined with the presumed cause of death (e.g., "sudden cardiac death").

If the death is attributed to progression of UC, "ulcerative colitis progression" should be recorded on the Adverse Event eCRF. If the death is attributed to progression of CD, "Crohn's disease progression" should be recorded on the Adverse Event eCRF.

Deaths that occur after the adverse event reporting period should be reported as described in Section 5.6.

5.3.5.10 Preexisting Medical Conditions

A preexisting medical condition is one that is present at the screening (Study Week 0) visit for this study. Such conditions should be recorded on the General Medical History and Baseline Conditions eCRF.

A preexisting medical condition should be recorded as an adverse event only if the frequency, severity, or character of the condition worsens during the study. When recording such events on the Adverse Event eCRF, it is important to convey the concept that the preexisting condition has changed by including applicable descriptors (e.g., "more frequent headaches").

5.3.5.11 Lack of Efficacy or Worsening of Ulcerative Colitis or Crohn's Disease

Events that are clearly consistent with the expected pattern of progression of the underlying disease should not be recorded as adverse events. These data will be captured as efficacy assessment data only. In most cases, the expected pattern of progression will be based on the MCS for patients with UC and the SES-CD for patients with CD, which includes endoscopic disease evaluation. In rare cases, the determination of clinical progression will be based on symptomatic deterioration. However, every effort should be made to document progression through use of objective criteria. If there is any uncertainty as to whether an event is due to disease progression, it should be reported as an adverse event.

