3.1.5 Disease Evaluation Visits

Patients with worsening disease, as determined by the investigator, should return to the clinic as soon as possible for a disease evaluation visit. The investigator may also schedule a disease evaluation visit to determine if a patient has achieved clinical remission. Patients with UC will undergo a flexible sigmoidoscopy and MCS evaluation at the disease evaluation visit. Patients with CD will undergo an ileocolonoscopy and CDAI evaluation, with one exception: Patients who experience worsening disease while receiving efmarodocokin alfa will not undergo an ileocolonoscopy unless the visit corresponds to a time when an ileocolonoscopy is already scheduled to occur.

After determination of the patient's disease status, the investigator may initiate or discontinue treatment with efmarodocokin alfa as appropriate (see efmarodocokin alfa treatment algorithm in [Table 2](#)).

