4.6 TREATMENT, PATIENT, STUDY, AND SITE DISCONTINUATION

4.6.1 Study Treatment Discontinuation

Patients must permanently discontinue study drug if they experience any of the following:

- Any medical condition that the investigator or Sponsor determines may jeopardize the patient's safety if he or she continues to receive study drug
- Investigator or Sponsor determines it is in the best interest of the patient
- Pregnancy
- Drug-related anaphylaxis or other severe (Grade 3 or 4) drug-related hypersensitivity reaction
- Unresectable colonic mucosal dysplasia
- High-grade colonic mucosal dysplasia or colon cancer
- Requirement for rescue therapy outside defined limits of the protocol (see Section 4.4.1)
- Inability to tolerate corticosteroid taper (see Section 3.1.7)
- Disease flare (as defined in Section 3.1.4.4) while receiving efmarodocokin alfa
- Disease worsening as a result of efmarodocokin alfa treatment, in the investigator's judgment
- Malignancy or cervical Pap test with cervical intraepithelial neoplasia (CIN) of Grade >1, adenocarcinoma in situ (AIS), or high-grade squamous intraepithelial lesions (HSILs)
- De novo or reactivated serious viral infection, such as hepatitis B virus, hepatitis C virus, HIV, disseminated varicella zoster virus, or disseminated herpes simplex virus. For other serious or severe infections, see Section 5.1.2.3 and Table 4.
- Severe liver injury as defined by Hy's Law (see Section 5.3.5.7)
- *Grade 4 thromboembolism or deep vein thrombosis*

The primary reason for study treatment discontinuation should be documented on the appropriate eCRF. Patients who receive at least one dose of efmarodocokin alfa must

undergo safety follow-up assessments 8 weeks after their final dose of study drug (see Section 3.1.6 and [Appendix 1](#) for more information).

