5.3.5.12 Hospitalization or Prolonged Hospitalization

Any adverse event that results in hospitalization (i.e., inpatient admission to a hospital) or prolonged hospitalization should be documented and reported as a serious adverse event (per the definition of serious adverse event in Section 5.2.2), except as outlined below.

An event that leads to hospitalization under the following circumstances should not be reported as an adverse event or a serious adverse event:

- Planned hospitalization required by the protocol (e.g., for study drug administration, insertion of access device for study drug administration, or procedure required by the study)
- Hospitalization for a preexisting condition, provided that all of the following criteria are met:

The hospitalization was planned prior to the study or was scheduled during the study when elective surgery became necessary because of the expected normal progression of the disease

The patient has not experienced an adverse event

An event that leads to hospitalization under the following circumstances is not considered to be a serious adverse event, but should be reported as an adverse event instead:

- Hospitalization that was necessary because of patient requirement for outpatient care outside of normal outpatient clinic operating hours

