6.5 EXPLORATORY EFFICACY ANALYSES

The analysis population for the efficacy analyses will consist of all patients.

The exploratory efficacy endpoints will be summarized by descriptive statistics based on the following calculations, with clinical response and clinical remission as defined in Sections 3.1.4.2 and 3.1.4.3.

- Proportion of patients with a clinical response
- Proportion of patients with a clinical remission
- Time from clinical remission to loss of clinical remission
- Change from baseline (i.e., either the baseline score in the parent study or the last score prior to initiation of the most recent course of efmarodocokin alfa 60 µg/kg IV Q4W during the extension study, whichever score is the most recent) in PRO2 for patients with CD

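### Worsening of UC or CD classed as expected progression can be left out of the SAE and AESI counts, and no planned analysis counts on-drug flare or worsening as an event.

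*Combined protocol and SAP*

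**What the plan says.** **Recording of worsening.** Section 5.3.5.11 reads: "Events that are clearly consistent with the expected pattern of progression of the underlying disease should not be recorded as adverse events". It continues: "These data will be captured as efficacy assessment data only". It then limits the exclusion: "If there is any uncertainty as to whether an event is due to disease progression, it should be reported as an adverse event". Section 5.3.5.9 requires deaths from progression of UC or CD to be recorded as adverse events. Section 5.3.5.10 says: "A preexisting medical condition should be recorded as an adverse event only if the frequency, severity, or character of the condition worsens during the study". Section 5.2.1 counts exacerbation of an existing disease as an adverse event and refers the reader to 5.3.5.10 and 5.3.5.11.

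**What worsening does to treatment.** Table 2 and Section 4.6.1 require permanent discontinuation for a protocol-defined flare on drug and for this: "Disease worsening as a result of efmarodocokin alfa treatment, in the investigator's judgment".

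**What is analysed.** Table 1 and Section 6.5 list clinical response, clinical remission, "Time from clinical remission to loss of clinical remission", and change in PRO2 for patients with CD. Section 6.4 describes adverse events, laboratory results and clinical data by exposure. Section 6.2 summarizes reasons for study withdrawal and counts withdrawals as non-responders. Section 4.6.1 has the primary reason for stopping treatment entered on the eCRF, but no section specifies a summary of it.

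**The concern.** The study exists to describe long-term safety and tolerability, without a control arm and with open-label assessment. In that setting, worsening colitis is hard to tell apart from lack of effect. The plan removes the clearly expected cases from adverse events and assigns them to efficacy, but the efficacy section has no analysis that counts them. A reader of the report could not say how many patients flared on drug, when they did so, or how many stopped treatment for that reason.

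The routes for serious and special-interest events do not restore these cases, because each starts from an adverse event. The hospitalization rule in Section 5.3.5.12 begins "Any adverse event that results in hospitalization". The AESI in Section 5.2.3 for stopping study drug likewise requires an adverse event. An event classed as expected progression can miss both.

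**Working it through.** **1. Does another analysis identify on-drug flare or worsening?**

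- *Time to loss of remission.* Table 2 gives drug only to patients who are not in clinical remission. A patient who flares on drug has generally no current remission to lose, so the event falls outside this endpoint. For scale, Section 6.1 assumes 20% of 135 patients in sustained remission: 0.20 × 135 = 27, leaving 135 − 27 = 108 who could not contribute. This treats the sustained-remission rate as the rate of ever reaching remission, which is an assumption.
- *Response and remission.* A patient who worsens and withdraws is a non-responder under Section 6.2. So is a patient who simply did not improve. The two cannot be separated.
- *PRO2.* This covers CD only and gives a mean change, not an event count.
- *Disposition.* Section 6.2 tabulates reasons for leaving the study. Appendix 1, footnote g, sends patients who stop drug for a Section 4.6.1 reason to an early termination visit, so some cases may show there. The reason for stopping treatment is a separate eCRF item with no table.
- *Off-drug flare.* Observation is for patients in remission. UC remission (3.1.4.3) needs the other Mayo subscores at 1 or below, while UC flare (3.1.4.4) needs an endoscopy subscore of 2 or more. CD remission needs CDAI below 150, while CD flare needs 220 or more. Apart from local versus central endoscopy reads in UC, an off-drug flare is also a loss of remission. Time to loss of remission therefore largely captures it, though not labelled as a flare.

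**2. Does seriousness or stopping treatment override the exclusion?**

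Section 5.3.5.9 overrides it for death. Nothing comparable is stated for hospitalization, another seriousness criterion, or permanent discontinuation. Sections 5.2.2, 5.2.3 and 5.3.5.12 all presuppose an adverse event.

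**3. How large could the effect be?**

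Inputs from Section 6.1: n = 0.50 × 270 = 135; benchmark SAE rates 13/198 = 6.6% and 37/275 = 13.5%.

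The plan's intervals reproduce with the exact (Clopper-Pearson) method, with limits Beta(0.025; x, n − x + 1) and Beta(0.975; x + 1, n − x):

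| Rate | x = rate × 135 | Exact 95% CI | Plan |
|---|---|---|---|
| 6.6% | 8.91 | 3.0% to 12.2% | 3% to 12% |
| 13.5% | 18.225 | 8.2% to 20.4% | 8% to 20% |

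Next, take 18 patients with an SAE and remove an **assumed** share as expected progression:

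| Share removed | Patients left | Rate | Exact 95% CI |
|---|---|---|---|
| none | 18/135 | 13.3% | 8.1% to 20.3% |
| one third | 18 − 6 = 12/135 | 8.9% | 4.7% to 15.0% |
| one half | 18 − 9 = 9/135 | 6.7% | 3.1% to 12.3% |

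The documents give no flare rate and no rate of admission for UC or CD, so the share is not an estimate. No sample-size figure changes.

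**The case against.** **The exclusion is narrow.** It covers only clear cases, and doubtful ones must be reported. This stands. Worsening that the investigator blames on the drug is hard to call expected progression, fits Section 5.2.1, and should already be an adverse event. Section 5.3.5.11 does not say so, and a sentence would settle it.

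**A reader might infer that Section 5.3.5.11 contradicts Section 5.2.1.** It does not. Section 5.2.1 refers to 5.3.5.11 for this very item, which makes it a general rule with a specific exception.

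**A reader might infer that these patients vanish from the results, or that off-drug flare goes unreported.** Neither is supported. They appear indirectly, as set out in step 1, and off-drug flare is largely a loss of remission.

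**A reader might state as fact that a hospitalized flare is not an SAE.** The text is ambiguous. Section 5.3.5.12 lists the admissions that need not be reported, and an unplanned admission for flare is not among them. Yet its opening rule applies only to adverse events, so a site that has classed the flare as expected can read it either way.

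**CD endoscopy.** Section 5.3.5.11 rests the CD judgment mostly on the SES-CD, while Section 3.1.5 says "Patients who experience worsening disease while receiving efmarodocokin alfa will not undergo an ileocolonoscopy" unless one is already scheduled. It is tempting to conclude that CD worsening will be wrongly called expected. Missing endoscopy adds uncertainty, however, and uncertainty sends the case to adverse event reporting.

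**Section 6.4 is open-ended.** It allows clinical data to be summarized beyond its list. It permits a flare table but does not commit the sponsor to one.

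**Conclusion.** The point holds in a limited form. On-drug flare and worsening are not identifiable as events in either the safety or the efficacy summary. Serious or treatment-ending worsening that a site classes as clearly expected can be left out of the SAE and AESI counts. The direction is towards understatement.

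The size cannot be derived from the documents. The fall from 13.3% to 8.9% or 6.7% depends wholly on the assumed share of one third to one half and on every such case being classed as expected. A reader might infer that classification would carry the result from the plan's higher benchmark to its lower one. That follows from the chosen share, and the documents do not say how the two benchmark placebo arms handled UC worsening.

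This is an inexpensive improvement to reporting and wording. It does not show a flaw in the sample size or the treatment algorithm.

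**What to change.** 1. **Sections 6.4 and 6.5.** Add a descriptive table, split by on-drug and off-drug time, of the number, proportion and timing of protocol-defined flares (3.1.4.4) and of investigator-attributed drug-related worsening. Add a table of reasons for study treatment discontinuation. The flare components and discontinuation reasons are already collected.
2. **Section 5.3.5.11.** State that worsening within the adverse event reporting period is recorded as an adverse event when it meets a seriousness criterion, leads to permanent discontinuation of study drug, or is judged to result from study drug. Make Sections 5.2.3 and 5.3.5.12 consistent with this. Show adverse event tables with and without UC/CD worsening terms, so that readers can see both views.

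The documents describe no separate form for hospitalization due to UC or CD. Those admissions can be summarized through the adverse event records that item 2 creates. Item 2 cannot reach flares later than 8 weeks after the final dose, when routine adverse event reporting has ended (5.3.1); the flare table in item 1 covers those.

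**Cost.** Protocol wording, the two tables, some added adverse event entries, and slightly less favourable adverse event and SAE rates. No treatment or stopping rule changes.
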